3T Protocol+Impact Analysis Plan		
Version: 2.0		Last updated: 3.8.23

3T: TUNE IN! TURN ON! TURN UP!

PROTOCOL WITH IMPACT ANALYSIS PLAN

Purpose (Brief description)
The purpose of this protocol and analysis plan template is to document the research questions, study design, study methods, and programmatic information along with the planned impact and supplemental analyses. All sections in this analysis plan are intended to elicit text that can be directly copied into final evaluation reports or journal articles. Deviations from these plans are to be discussed and documented for transparency.
Primary Author(s)
3T Study Team, ETR Associates and dfusion, Inc.
3T Clinical Trials Registration #: NCT04135443

Public Health Narrative (Excerpt from Phase II Proposal)

Black men who have sex with men (BMSM) have been disproportionately affected by HIV/AIDS epidemic. Nearly half of the 1.2 million individuals living with HIV in the United States are African American, even though African Americans represent only 12% of the U.S. population. In 2009, Black MSM represented 73% of new HIV infections among Black men, and more new HIV infections occurred among young Black MSM (aged 13-24) than any other age and racial group of MSM, with an increase of 87% from 2005-2014. Young Black MSM (between the ages of 13 and 24) are more than twice as likely to be infected with HIV than young MSM of any other ethnic group. Yet there is a lack of school-based sexual education for this group of young people and few HIV interventions designed specifically to meet the needs of young BMSM. This project will develop a mobile app based multimedia interactive HIV/STI and sexual health intervention developed for use by YBMSM ages 14- 19 that delivers the intervention as a series of interactive activities tailored to the user and employs a theory based approach to address essential knowledge, perceptions of risk, peer norms, attitudes and skill with two primary goals: (1) To reduce HIV/STIs, it emphasizes partner reduction, avoidance of concurrent partners, condom use and HIV/STI tests; and (2) To improve sexual health, it helps participants to become clearer about what they do/don't want to do sexually, to communicate their choices, and to learn ways to enhance sexual experience without increasing HIV/STI risk.

3T Protocol+Impact Analysis Plan		
Version: 2.0		Last updated: 3.8.23

1) Research Questions That Address Program Effectiveness on Behavioral Outcomes

These are consistent with outcomes listed on the www.ClinicalTrials.gov website.

a. Primary research question(s):

- i.* What is the impact of the 3T app relative to the 3T control website on the number of times engaged in condomless receptive or insertive anal intercourse or condomless vaginal intercourse in the last 3 months at follow-up, approximately 3 months post baseline.

b. Secondary research question(s):

Assessed at the 3-month follow-up (note: had to drop 6-month follow-up due to impact of COVID on study progress and timeline)

- i.* What is the impact of the 3T app relative to the 3T control website on the **number of times participants reported having been tested for STI, including HIV in the last 3 months?**
- ii.* What is the impact of the 3T app relative to the 3T control website on **communication with a partner about sexual desires/behavior?** (Dyadic Communication Scale)
- iii.* What is the impact of the 3T app relative to the 3T control website on **condom attitudes?** (Condom Attitude Scale for Adolescents)
- iv.* What is the impact of the 3T app relative to the 3T control website on condom use self-efficacy? (Sexual Risk Behavior Beliefs and Self-Efficacy Scale)
- v.* What is the impact of the 3T app relative to the 3T control website on attitudes toward lube?

c. Dropped outcomes:

The following secondary outcome was dropped before the study launch and was not asked on the survey in a way that allowed this calculation:

- i.* What is the impact of the 3T app relative to the 3T control website on the **number of partners with whom had anal or vaginal sex without using condoms in the last 3 months?**

2) Description of the Intended Intervention and the Attention Control Conditions

[figure not shown]
[figure not shown]
Intervention condition: The intervention is a mobile app delivered sexual health promotion program designed specifically for young black men who have sex with men or

3T Protocol+Impact Analysis Plan		
Version: 2.0		Last updated: 3.8.23

who are attracted to men. The mobile app includes 36 interactive activities including resource maps, pre-exposure prophylaxis (PrEP) and post-exposure prophylaxis (PEP) content, and an asynchronous communication forum. The app helps participants to become clearer about what they do/don't want to do sexually, to communicate their choices. It also focuses on ways to increase healthy relationships, enhance sexual experience if having sex while reducing HIV/STI risk.

Attention control condition: The control intervention featured a website containing seven health promotion materials in online pamphlet or post formats focusing on mental health (2 pamphlets), nutrition (2 pamphlets), relationships (2 pamphlets) and COVID (1 poster). Young people were asked to select 4 materials to review as part of their participation.

- Mental Health
 - 5 Ways to Stop Stress
 - Suicide Talk, What To Do If You Hear It
- Nutrition
 - Eating Well With No Time & No Money
 - What's a Serving? Choose healthy serving sizes to stay at a healthy weight.
- Relationships
 - Yes Means Yes, What is Affirmative Consent?
 - Relationship Check, Healthy or Un?
- COVID
 - Actions to Protect Yourself and Others

Study Design

a. Sample

The study was open to participants who self-identify as male, Black, African American, or biracial Black/African American; report being ages 14-19 at baseline; self-identify as cisgender male; report sexual attraction to men; and reside in any state in the United States. The age range was expanded to include young people ages 18-19 in May 2022 after facing significant COVID-related challenges in recruiting young people in the 14–17-year age range.

b. Recruitment approaches

The study went through four distinct recruitment phases to accrue the sample (Table 2). Recruitment was impacted severely by the COVID pandemic, requiring multiple pivots in recruitment plans over a two-year period spanning August 2020 to July 2022. After facing COVID-related and other challenges in our proposed recruitment approaches, the study sample was secured through paid advertising on social networking sites.

Table 2. 3T Recruitment Phases

Phase	Dates	Recruitment Focus	Results
Phase 1: CBO recruitment partners	August- November 2020	We engaged selected CBOs to do direct recruitment for the study through their networks and social media, referring interested youth to the 3T recruitment website directly. We had signed MOUs with the following CBOs: AIDS Alabama; the LGBTQ Center, Long Beach; Michigan Organization on Adolescent Health; Nashville Cares; and Triangle Empowerment Center.	We established MOUs with five agencies; agencies were enthusiastic about study but ultimately not successful in engaging youth due to challenges of COVID and its impact on youth engagement with agency services. No youth were recruited during this phase, and we pivoted to general social media strategies.
Phase 2: Broad social media and micro influencers	May 2021	We worked with Commando, a company specializing in social media study recruitment and ad placement for LGBTQ populations to use social media (Instagram) to promote the study nationally. At the same time, we identified a small number of micro influencers (2) who were paid to promote the study using IRB approved recruitment messages through their social media channels. We also tried TikTok and Snapchat but those platforms would not allow us to promote the study due to their restrictions on promoting studies (Snapchat) and promoting	Over 800 individuals completed the screener over the launch weekend in May 2021. Nearly all appeared to be out of country and age range but were claiming to be in age range and within the US. We closed recruitment and rejected all surveys coming in during this period because the sample was not our desired population. We also stopped general social media recruitment and moved toward a new phase of more targeted recruitment to avoid international and

		sexually related content (Tik Tok). We also planned to use a snowball sampling approach during this phase, which allowed young people to refer up to three others from their networks and receive a stipend if the individual met eligibility criteria.	national scam attacks. Further, we added an online video screening requirement for age and country verification for those who did screen as eligible. Further, we dropped use of social media influencers as their promotion also contributed to scam attacks. Finally, we also dropped snowball sampling to reduce scam attacks and because it was not yielding expected results in a different study. After this phase, we considered and explored other avenues (e.g., schools and school clubs such as GSAs) but COVID continued to impact schools' and agencies' ability to reach youth and engage with us.
Phase 3: Change in study design to conduct study directly at CBOs	November 2021-March 2022	We shifted our study design to work with direct service CBOs who serve the study population. The design involved training staff to recruit for the study and then invite young people to the site where study staff would have participants engage with their assigned app or website and complete the intervention while at the agencies. We aimed to recruit 1-2 sites near each of two project advocate staff members (1-2 in Atlanta or MS and 1-2 in TX) to minimize travel expenses and maximize the number of times we might be able to host young people at the sites.	Up to 4 agencies expressed interest and then could not move forward because they were not seeing/serving enough young people who met the inclusion criteria at their agencies. This alternate design was then dropped. We discussed and decided to return to using paid advertising and shifted our age of eligibility to include 18- and 19-year-olds, seeking IRB approval to recruit via Grindr, Jack'd and Scruff.
Phase 4: Paid advertising via social networking sites (Grindr, Jack'd/Scruff)	Grindr inbox ad: May 24, 2022 (12 states) Jack'd/Scruff ads: May 2022 and July 2022 (National)	We re-engaged with Commando, an agency specializing in paid advertising for studies centering LBBTQ populations with the new study age criteria. They prepared ads and placed them during the designated time frames.	Screened 2,047. Enrolled 178 eligible participants who completed baseline (see final flow diagram for specifics).

c. Screening criteria and process

Participants were invited to complete a screening survey (via Qualtrics) that assessed eligibility for the study. Those who did not meet eligibility criteria received an immediate message thanking them for this interest in the study and informing them that they were not eligible for participation. Those who met eligibility criteria were forwarded to the study consent form and asked to read and complete the form to indicate their interest in taking part. (Note: As noted below: The IRB approved a waiver of parental consent for those ages 14-17).

d. Consent process

Participants who screened into the study were directed to an online assent (14-17) or consent (18-19) form that explained the study expectations along with risks and benefits. The IRB approved a waiver of parental consent for participants ages 14-17). Participants were asked to provide their consent if interested in taking part by clicking “yes” on the consent form and providing basic contact information (mobile number for texting and email as well as a question on which was their preferred method of contact). Those who provided affirmative consent went through a further confirmation protocol to reduce the risk for bots, scams, or those out of the country to enroll. The protocol included review of metrics from Qualtrics’ internal fraud detection system, ReCAPTCHA and Scamalytics. All prospective participants whose application was flagged as follow were rejected:

Indicator	Reject if
RelevantIDDuplicate	True/1
RelevantIDDuplicateScore	>75
RecaptchaScore	<.5
RelevantIDFraudScore	>30
BallotBoxStuffing	True/1

Young people also were given a chance to indicate they needed more information before making a study decision. Those who marked that option were asked to provide contact information so a study ambassador could follow-up to address any unanswered questions. Once participants’ eligibility, consent, and geographic location (US) were confirmed, participants received a link to the baseline survey.

e. Random assignment process

The 2-arm randomized controlled trial involves randomizing individual participants using an equal allocation (allocation ratio 1:1) to receive the 3T app or access to the attention control website. Participants were randomized after completing their baseline surveys using the randomizer feature of Qualtrics.

f. **Baseline and follow-up data collection**

The primary source of data for the outcome analyses is the self-report survey. The survey was administered two times: Baseline and 3-months post-baseline. The original study design included a 6-month follow-up timepoint that had to be dropped because of delays and challenges in getting the study launched during COVID.

Data collection was ongoing due to rolling enrollment. Surveys were primarily distributed by SMS message. Shortly after their screener responses were reviewed and approved, prospective participants received a text message containing an explanatory message and a link that would be them to the baseline survey on the Qualtrics platform. Follow-up surveys were sent out in a similar fashion approximately 1 month and 3 months post baseline. Participants who had not yet completed a survey automatically received up to 5 reminders for survey completion in addition to their initial invitation. In cases where the Qualtrics system indicated an SMS message bounced, email invitations to take the survey were attempted.

3) **Analysis**

Table 3. Behavioral outcomes used for primary impact analyses research questions.

Outcome name	Description of the outcome, including how it is operationalized (e.g. “The outcome is a yes/no response taken directly from the survey” or “the risk outcome is calculated as the average of the five risk indicator variables”).	Source of the measure (e.g. performance measure)	Timing of measure (e.g., 6 months after program ends)
i. Number of times engaged in condomless receptive or insertive anal intercourse or condomless vaginal intercourse in the last 3 months at follow-up, approximately 3 months ^a	Count of condomless receptive anal, insertive anal, and/or vaginal sex acts with main partners and casual partners. Note: Participants who report they have never had sex or did not have sex in past 3 months (anal or vaginal) are assigned a 0. Constructed from the following variables (both T1 and T3 were used but only T3 is listed): T3_Q69_1 and T3_Q95_1 (insertive anal, no condom); T3_Q69_3 and T3_Q95_3 (receptive anal, no condom); T3_Q69_5 and T3_Q95_7 (insertive vaginal, no condom); T3_Q29 (EVER had vaginal/anal sex); T3_Q30 (had vaginal/anal sex in last 3 months).	Outcome survey	3 months following baseline

^a This outcome was assigned a value of 0 if a respondent reported they have never had that type of sex or didn't have that type of sex in the past 3 months. This allows for the full sample to be included in analytic models. This outcome will be dichotomized if the distribution is highly skewed.

Table 4. Behavioral and attitudinal outcomes used for secondary impact analyses research questions.

Outcome name	Description of the outcome, including how it is operationalized (e.g. "The outcome is a yes/no response taken directly from the survey" or "the risk outcome is calculated as the average of the five risk indicator variables").	Source of the measure (e.g. performance measure)	Timing of measure (e.g., 6 months after program ends)
i. Number of times participants reported having been tested for HIV in the last 3 months ^a	Count of number of times reported being tested for HIV in the last 3 months. Constructed from T1_Q55/T3_Q55 (how many times tested for HIV in last 3 months).	Outcome survey	3 months post baseline
ii. Number of times participants reported having been tested for STIs (excluding HIV) in the last 3 months ^a	Count of number of times reported being tested for STIs other than HIV in the last 3 months. Constructed from T3_Q58 (how many times tested for an STI/STDs in last 3 months).	Outcome survey	3 months post baseline
iii. Sexual Communication Self-Efficacy scale	Average of 20 items on a 4-point scale (1 to 4), with a range of 4 - 80, with a higher score indicating better outcomes. Calculate the average if at least 50% of items were answered (10 of 20). Items embedded in and drawn from questions Q46, Q94, Q47, Q48 and Q49.	Outcome survey	3 months post baseline
iv. Condom Attitudes Scale for Adolescents	Average of 21 items on a 4-point scale (1 to 4) with a range from 21 to 84 with higher scores indicating better outcomes. (Two items were omitted from the original 23-item scale.) Ten questions are reverse coded. Items embedded in and drawn from questions Q40 and Q93.	Outcome measure	3 months post baseline
v. Condom use self-efficacy	Average of 4 items adapted from the Sexual Risk Behavior Beliefs and Self-Efficacy Scale scored on a 4-point scale (1 to 4) with a range from 4 to 16 with higher scores indicating better outcomes. Items embedded in and drawn from question Q42.	Outcome measure	3 months post baseline
i. Attitudes towards lube	Average of 3 items on openness to using sexual lubricant on a scale from 1 to 4 with higher scores indicating more positive views towards		

3T Protocol+Impact Analysis Plan		
Version: 2.0		Last updated: 3.8.23

lube (better outcome). The third item is reverse coded. Items embedded in and drawn from question Q41.

^a If an outcome assessing the number of times has a very skewed distribution, it may be collapsed into a dichotomous variable (e.g, 0 times, 1 or more times) based on the final distribution.

a. Analytic sample

We will use complete case analysis as the benchmark sample for this study. The analytic samples for both primary and secondary outcomes will include all individuals who respond to the questions making up the outcomes at baseline and follow-up and have complete data on the covariates included in each model.

b. Data cleaning

Missing data. We will examine missingness of potential covariates and use data from the follow-up survey to fill in missing values from baseline on covariates that are hypothesized not to change between the two survey timepoints. The primary and secondary outcomes will be analyzed using complete cases.

Inconsistencies. Because of forced skip patterns pre-programmed into the electronic data collection devices, we expect the sexual behavior outcome data to be relatively clean within time points. *Within time* consistencies will be checked on questions asking about the type of sex had in the last 3 months and the number of times respondents had the type of sex across all partners. For respondents with inconsistencies, we will assess patterns across all variables and discuss decision rules. *Across time* inconsistency will be checked on questions asking whether respondents have ever had vaginal or anal sex. With only two data points, we will analyze the data with and without inconsistent cases.

Extreme values. For questions asking about the number of times a behavior occurred we will examine extreme values in the context of other responses and apply a consistent decision rule.

c. Assessment of baseline equivalence

In addition to the baseline measures of the outcomes, we also will assess equivalence of the intervention and control groups at baseline on age and having a main partner. To assess equivalence between groups on each of these variables, we used regression analyses with the variable of interest as the dependent variable and the intervention indicator as the independent variable. The groups are considered not equivalent on a given variable if the *p*-value for the intervention indicator's regression coefficient is < 0.05 using the Wald test.

d. Condition crossover and contamination

An intent to treat model will be used in the analysis so that participants will be analyzed as randomized to treatment or control and followed up regardless of whether they interact with participants in the other condition.

3T Protocol+Impact Analysis Plan		
Version: 2.0		Last updated: 3.8.23

e. **Analytic approach for primary research questions**

i. **Model specification:**

SPSS will be used to conduct the descriptive and bivariate analyses as well as the multivariable analyses. Statistical significance levels will be set at $p < .05$ unless otherwise noted.

Separate data analyses will be performed on each outcome variable named above and will progress through the following stages:

First, *descriptive analyses* will be used to explore the data on all model variables at baseline and follow up for distributional assumptions and unanticipated patterns that might affect subsequent analyses. For example, as noted in the outcomes table, some outcomes may need to be dichotomized if the distribution is too skewed towards 0.

Second, *bivariate analyses* will be used (1) to compare the baseline demographic and background characteristics of the intervention and control groups and (2) to test for relationships between the outcome variable and potential covariates (confounders) being measures. A potential covariate will be included in the model if: (1) the variable is associated with the condition indicator at $p < 0.15$; and (2) the variable is associated with the outcome at $p < 0.15$ in ***individual bivariate analyses***. Our plan for covariate screening is derived from those suggested in Altman (1991) and Hosmer and Lemeshow (1989). In the latter, it is suggested that $p < .25$ as a screening criterion may be more appropriate than $p < .05$ because the latter often fails to identify variables that may be important to control. We have traditionally “split the difference” and selected a $p < .15$ to preserve degrees of freedom of the model. We routinely include the baseline value of the outcome regardless of screening criteria (Pocock et al, 2002). Below, we clarify which covariates will be included regardless of these screening criteria. (4) Bivariate analyses will also be conducted to assess baseline equivalence for the final primary analytic samples.

Third, *multivariable analyses* will be conducted using regression analyses (linear or logistic) to evaluate the research questions as definitively as possible.

Each model will include an indicator variable denoting (1) intervention group, (2) the baseline outcome variable, (3) the number of days between the baseline and follow-up survey (if there is a large range), (4) age at baseline, and (5) a set of *a priori* demographics and outcome-related covariates that screened positively as candidates for inclusion in the bivariate screening step.

Covariates

Covariates to be forced into all models on an *a priori* basis:

1. Baseline value of outcome
2. Actual # of days between baseline and follow-up

3T Protocol+Impact Analysis Plan		
Version: 2.0		Last updated: 3.8.23

3. Age at baseline

Race was not included as it was a study eligibility requirement (black identifying).

A priori covariates to be screened into the models:

1. With whom have had sex (cis men only vs cis men+others)
2. Effect of COVID pandemic on their ability to see a romantic or sexual partner (0=not at all, 1=somewhat, 2=very).
3. Effect of COVID pandemic on ability to get condoms (0=not harder, 1=may or may not be harder, 3=harder).
4. Has a main partner.

NOTE: if there is high correlation ($r > .5$) between some of these indicators we will not include them all.

ii. Sample attrition

Attrition analyses will be conducted to examine the rate of attrition by condition. Results from the attrition analyses will help evaluate the need to temper interpretations of outcome results.

iii. Sensitivity analyses

- (1) Sensitivity analyses will be conducted examining the sub-group of participants with matching self-reported birthdates at baseline and the 3-month follow-up and within the allowable age range (14-20).

f. Analytic approach for secondary research questions

Analyses for secondary research questions will proceed using the same steps as described for the primary research questions.

4) Additional planned analyses

Additional exploratory analyses of the impact evaluation data may include the following.

- a. Subgroup analyses based on participants in each condition who used their respective interventions (use evident from log in data vs no use evident) may be completed for the primary and secondary outcome variables.
- b. Analyses of the following variables not specified as primary or secondary:
 - a. Lube Knowledge (which are safe w/latex condoms)
 - b. HIV Knowledge (includes PrEP and PEP awareness)
- c. Examination of impact on primary outcome for those reporting casual partners if sample size warrants this level of exploration.

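### The baseline covariate in the primary model scores recently inactive youth and consistent condom users alike as 0; forcing in baseline sexual activity (T1_Q30) would recover a small, uncertain amount of precision

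*Combined protocol and SAP*

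**What the plan says.** Table 3 (section 3, Analysis) defines the primary outcome as: "Count of condomless receptive anal, insertive anal, and/or vaginal sex acts with main partners and casual partners". It then states: "Participants who report they have never had sex or did not have sex in past 3 months (anal or vaginal) are assigned a 0". Footnote a to that table explains that this coding keeps the full sample in the models, and adds: "This outcome will be dichotomized if the distribution is highly skewed".

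The list of source variables carries the note "both T1 and T3 were used but only T3 is listed" and includes "T3_Q30 (had vaginal/anal sex in last 3 months". The baseline counterpart, T1_Q30, is therefore available.

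Section 3e.i forces three covariates into every model: "Baseline value of outcome", the number of days between surveys, and age. On the first it says: "We routinely include the baseline value of the outcome regardless of screening criteria". Four further covariates are screened: type of sexual partners, two COVID items, and having a main partner. A screened covariate enters only if it is associated with both the condition and the outcome at p < 0.15.

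On balance, section 3c covers the baseline outcome measures and says "we also will assess equivalence of the intervention and control groups at baseline on age and having a main partner". Section 3e.i also plans a comparison of baseline characteristics without naming the variables.

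**The concern.** Eligibility (Study Design, section a) requires attraction to men, not sexual activity, and the zero-coding footnote shows that the plan expects some inactive participants. A baseline 0 then mixes people who were not having sex with people who were having sex and using condoms. Their chances of a condomless act in the next 3 months plausibly differ, because the second group is already sexually active. A model that holds only the mixed baseline value gives both groups the same prediction, apart from what age and days between surveys explain.

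Two things are at stake. Variation that could be predicted stays in the error term. A chance difference between arms in the share of sexually active participants is also not fully adjusted for. Enrolment ended at 178 participants, so lost precision cannot be made up by recruiting more.

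**Working it through.** The plan states no sample size calculation, event rate, effect size or power, so there is no figure of its own to reproduce. From the documents come the coding rule, the covariate lists, 178 enrolled and 1:1 allocation. Every rate below is an assumption.

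**1. Does any planned covariate separate the two groups?** Age and days between surveys do not record activity. Partner type records with whom, not whether recently, and may be undefined for those who never had sex. The COVID items record difficulty in seeing partners or getting condoms. Having a main partner is a partial proxy, but under randomisation it passes the p < 0.15 test against condition only about 15% of the time, before the outcome test is applied. So the answer is no.

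**2. Gain if the outcome is dichotomised (linear-variance approximation).** Let wI, wC and wN be the baseline shares that are inactive, active without condomless acts, and active with condomless acts. Let pI, pC and pN be their probabilities of any condomless act at follow-up.

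- Extra variance explained by T1_Q30: G = wI·wC/(wI+wC)·(pC−pI)²
- Residual variance with T1_Q30: R = Σ w·p(1−p)
- Relative efficiency: (R+G)/R

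Assumed ranges: wI 0.30–0.50, wC 0.20–0.30, pI 0.05–0.15, pC 0.25–0.45, pN 0.50–0.80. The first three rows are the low corner, the midpoint and the high corner of these ranges. The last row is the midpoint with 15% inactive.

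| wI, wC, wN | pI, pC, pN | G | R | Relative efficiency |
|---|---|---|---|---|
| 0.30, 0.20, 0.50 | 0.15, 0.25, 0.50 | 0.0012 | 0.2008 | 1.01 |
| 0.40, 0.25, 0.35 | 0.10, 0.35, 0.65 | 0.0096 | 0.1725 | 1.06 |
| 0.50, 0.30, 0.20 | 0.05, 0.45, 0.80 | 0.0300 | 0.1300 | 1.23 |
| 0.15, 0.25, 0.60 | 0.10, 0.35, 0.65 | 0.0059 | 0.2069 | 1.03 |

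**3. Gain when the stability of behaviour is modelled.** A simulated population, with the linear model fitted with and without T1_Q30, gave these gains in effective sample size:

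- Dichotomised, with moderate stability (70–85% stay active, 20–40% start, 40–70% keep their condom pattern): about 0–3%.
- Dichotomised, with very stable activity (95% stay, 10% start) and condom use nearly unrelated over time (0–20% keep their pattern): about 10–30%.
- Count outcome: about 0–3% in every setting.

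**4. Power.** In logistic simulations with 142 analysed (about 80% of 178) and a log odds ratio of −1.0, power went from 0.62 to 0.65, from 0.51 to 0.55, and stayed at 0.66 in three scenarios with 30–50% inactive. With 15% inactive it went from 0.75 to 0.76, and with 10% it stayed at 0.77. A separate set of four scenarios gained about 0, 2, 2 and 7 points. By formula, for 50% v 35%, 89 per arm (178/2), baseline R² 0.20 and two-sided 0.05, power is 62.0% without T1_Q30, 63.5% with a 3.4% gain and 68.5% with a 16% gain.

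**5. Chance imbalance.** With 71 per arm and 30% inactive, the SE of the arm difference is √(2·0.3·0.7/71) = 0.077. A difference above 10 points then has probability 2·[1−Φ(0.10/0.077)] ≈ 0.19; with 89 per arm it is about 0.15.

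**The case against.** A reader might infer that a strongly prognostic variable has been left out and that the treatment comparison is therefore biased. The documents support neither step. They give no rate or correlation for Q30, and what counts is its value beyond the baseline outcome already in the model, which may be close to nothing. Randomisation protects the comparison from systematic bias.

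A reader might also infer that activity is not checked for balance at all. It is only not named: the baseline outcome is checked and is partly built from Q30, and the unspecified comparison in section 3e.i could include it. Nor would adding Q30 to the section 3c test do much. With 71 per arm and 30% inactive, the p < 0.05 rule flags only differences beyond 1.96 × 0.077 ≈ 15 points, so a 10-point imbalance (p ≈ 0.19) would pass.

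The other objections are about size, and they stand. The default outcome is the count, where the gain is about 0–3%. Recruitment in the final phase was by advertising on Grindr and Jack'd/Scruff, so the inactive share may be well below 30%. The variance formula is linear, while a dichotomised outcome would be analysed by logistic regression. For that reason the gain should not be presented as a number of extra participants.

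Finally, the covariate is not wholly free. With about 43 inactive participants (30% of 142), half per arm, a control risk of 0.05 and a log odds ratio of −1.0 (risk 0.019 in the app arm), the chance of no events among them is 0.95^21.5 × 0.981^21.5 ≈ 0.22. In that case the new coefficient would diverge, although the treatment estimate remains usable.

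None of this removes the core. The two groups share one code, nothing planned separates them, and the item that does is already in the data.

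**Conclusion.** The point holds as a modest improvement to the primary model, not as an error that invalidates it. The shared 0, the availability of T1_Q30 and its absence from both covariate lists can be read directly from Table 3 and section 3e.i. That T1_Q30 is prognostic is plausible from how the outcome is built, but no figure in the documents shows how strongly.

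The likely benefit is about 0–3% in effective sample size for the count. If the outcome is dichotomised it is typically a few percent, and 20% or more only under favourable assumptions. In power that is roughly 0–5 points, with about 7 in the most favourable case run. These sizes depend on the assumed inactive share, the follow-up risks, the stability of behaviour and about 80% retention. Protection against chance imbalance in activity comes in addition.

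**What to change.** Add one line to the covariates forced into the primary model in section 3e.i: any anal or vaginal sex in the 3 months before baseline (T1_Q30, yes/no). Code participants who never had sex (Q29) as no, so that a skipped Q30 does not drop them from the complete-case analysis.

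Do not put it on the screened list. The required association with condition at p < 0.15 would exclude it about 85% of the time (100% − 15%) under randomisation.

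If the outcome is dichotomised, baseline becomes a three-level factor: inactive, active without condomless acts, active with condomless acts. State in advance what will be done if the inactive group has almost no events, for example a penalised (Firth) logistic fit.

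Report T1_Q30 by arm descriptively in the baseline table, without a significance test.

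The cost is one degree of freedom and possible sparse cells; no new data are needed. Section 1 of the document asks for deviations to be documented, so record this as a dated change. If outcomes by arm have already been examined, present the adjusted model as a labelled additional analysis beside the planned one.
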